6.6 Vaccine Supply, Labeling, Storage and Tracking

The sponsor will ensure the following:

- Supply of the study vaccine(s).
- Appropriate labeling of all study vaccines provided that these comply with the legal requirements of each country where the study is to be performed.

The investigator must ensure the following:

- Acknowledge receipt of the study vaccines by a designated staff member at the site, including:
 - Confirmation that the vaccines were received in good condition
 - Confirmation to the sponsor or delegate of the temperature range during shipment from the sponsor to the investigator's designated storage location
 - In case of temperature excursions during shipment: Confirmation by the sponsor or delegate that the vaccines are authorized for use.
- Proper storage of the study vaccines, including:
 - Storage in a secure, locked, temperature-controlled location.

- Proper storage according to the instructions specified on the labels.
- Appropriate record keeping and inventory of the study vaccines, including regular documentation of adequate storage temperature.
- Appropriate use of the study vaccines, including:
 - Use only in accordance with the approved protocol.
 - Proper handling, including confirmation that the vaccine has not expired prior to administration.
 - Appropriate documentation of administration of vaccines to study subjects including:
 - Date, dosage, batch/lot numbers, expiration dates, unique identifying numbers assigned to subjects and study vaccines, and time of vaccine administration. This information will be maintained on the Vaccine Administration log that will be reviewed by the site monitor.
 - Reconciliation of all vaccines received from the sponsor. Reconciliation is defined as maintaining records of which and how many vaccines were received, which vaccines and the volume administered to subjects, which vaccines were destroyed at the site, and which vaccines were returned to the sponsor , as applicable.
- Proper adherence to the local institutional policy with respect to destruction of study vaccines upon approval from the sponsor.
- Complete record keeping of vaccine use, wastage, return or destruction, including documentation of:
 - Copy of the site's procedure for destruction of hazardous material.
 - Number of doses destroyed, date of destruction, destruction code (if available), method of destruction, and name of individual performing destruction upon approval from the sponsor.

Vaccines that have been stored differently from the manufacturer's indications **must not** be used unless the sponsor provides written authorization for use. In the event that the use cannot be authorized, the sponsor will make every effort to replace the vaccine supply. All vaccines used in conjunction with this protocol must be stored separately from normal hospital/practice stocks to prevent unintentional use of study vaccines outside of the clinical study setting.

Monitoring of vaccine accountability will be performed by the study monitor during site visits and at the completion of the study.

At the conclusion of the study, and as appropriate during the course of the study, the investigator must ensure that all unused study vaccines are destroyed locally (upon approval from sponsor) or returned to the sponsor.

7. ASSESSMENTS

7.1 Safety Assessment

The measures of safety used in this study are routine clinical procedures. They include a close vigilance for, and stringent reporting of, selected local and systemic adverse events routinely monitored in vaccine clinical studies as indicators of reactogenicity.

An AE is defined as any untoward medical occurrence in a subject or clinical investigation subject administered a pharmaceutical product at any dose that does not necessarily have to have a causal relationship with this treatment. Therefore, an AE can be any unfavorable and unintended sign (including an abnormal laboratory finding, for example), symptom, or disease temporally associated with the use of an investigational product, whether or not considered related to the investigational product. This definition includes intercurrent illnesses or injuries and exacerbation of pre-existing conditions.

The period of observation for AEs extends from the time the subject signs informed consent /assent until he or she completes the specified safety follow-up period visit 7 (Day 387) or terminates the study early (whichever comes first). AEs occurring after the ICF/assent is signed but prior to receiving study vaccine/product will be documented as an adverse event in EDC and recorded within the source document. However, any AEs occurring prior to receipt of any study vaccine will be analyzed separately from “treatment emergent” AEs (AEs occurring after administration of the first study vaccine).

AEs are collected as either solicited or unsolicited adverse events. Solicited events are derived from organized data collection systems, such as subject diaries or interview.

7.1.1 Solicited Adverse Events

The term “reactogenicity” refers to solicited signs and symptoms (“solicited adverse events”) occurring in the hours and days following a vaccination, to be collected by the subject’s parent(s)/LAR(s)/caregiver for 7 consecutive days, using a pre-defined Subject Diary Card. In this study there will be 2 versions of the Subject Diary Card; one version for children <3 years and one version for children ages 3 years and older.

The following solicited adverse events are included in the Subject Diary Card. Each adverse event is to be assessed according to defined severity grading scales.

For children ages 6 months through <3 years, solicited local AEs will include injection-site erythema, injection-site induration, injection-site ecchymosis, and injection-site tenderness; solicited systemic AEs will include change in eating habits, shivering, sleepiness, irritability, vomiting, diarrhea, and body temperature $\geq 38.0^{\circ}\text{C}$.

For children ages 3 years and older, solicited local AEs will include injection-site erythema, injection-site induration, injection-site ecchymosis, and injection-site pain; solicited systemic AEs will include loss of appetite, nausea, fatigue, malaise, generalized myalgia, generalized arthralgia, headache, shivering/chills, vomiting, diarrhea, and body temperature $\geq 38.0^{\circ}\text{C}$.

Solicited local or systemic adverse event continuing beyond Day 7 after vaccination, must also be recorded as an unsolicited AE on the AE eCRF.

Other Indicators of Reactogenicity

The use of analgesics/antipyretics will be captured as “absent” or “present” and will also be summarized by “for treatment” or “for prophylaxis”.

Instructions for Temperature Collection

Temperature should preferably be measured using the thermometer provided to the parent(s)/LAR(s) by the site staff. Ideally the subject’s temperature should be taken orally, however if for some reason it cannot be taken in this way, the alternate route of administration should be recorded on the Subject Diary Card.

The parent(s)/LAR(s) should be advised to begin measuring the subject’s temperature approximately 6 hours after the vaccination or prior to the subject going to bed if this is before. For the next 6 days following vaccination, the subject’s temperature should be measured at least once a day, preferably in the evening and at the same time each day. If the subject feels warm or unusually cold at any time during the 7 day post vaccination reporting period, the parent(s)/LAR(s) should be advised to record an additional temperature. If multiple temperatures are collected on any given day, only the highest temperature measured that day should be recorded.

If the subject’s temperature is below 35.5°C the parent(s)/LAR(s) should be advised to take a repeat measurement to ensure the temperature is correct. If the subject’s temperature is 38.0°C or higher at day 7, the parent(s)/LAR(s) should continue to measure the subject’s temperature each day until it returns below 38.0°C . The date of the last day that the subject’s temperature was above 38.0°C should be recorded on the Subject Diary Card.

If the subject’s temperature is $\geq 38.0^{\circ}\text{C}$ and is accompanied by one or more of the following symptoms: cough, sore throat, nasal congestion or runny nose, the parent(s)/LAR(s) should be advised to contact the study site immediately.

Instructions for Recording Injection Site Reactions

It is important to advise the parent(s)/LAR(s) that they should record both when an injection site reaction was observed as well as when one was not by checking the

appropriate tick box on the Subject Diary Card. The parent(s)/LAR(s) should be advised to complete their assessments at approximately the same time each day, preferably in the evening.

When a measurable reaction is observed such as hardness, bruising or redness the parent(s)/LAR(s) making the assessment should use the ruler provided by the site to measure the size in mm of the affected area. This information should be recorded by the parent(s)/LAR(s) on the Subject Diary Card.

When tenderness at the reaction site is noticed the parent(s)/LAR(s) should monitor the monitor the symptoms throughout the day and enter the most severe status that was observed (ie, mild, moderate or severe). If a reaction continues past day 7 the subject's parent(s)/LAR(s) should be advised to record the last day that the reaction was observed.

Instructions for Recording General Symptoms (changes in eating habits, sleepiness, vomiting, diarrhea, irritability and shivering)

When general symptoms are observed by the subject's parent(s)/LAR(s) they should be monitored throughout the day and the most severe status observed (mild, moderate or severe) should be recorded on the Subject Diary Card. Definitions of these categories for each the general symptoms inquired about can be found in the diary. It is important to advise the parent(s)/LAR(s) that they should record both when a reaction was observed as well as when one wasn't by checking the appropriate tick box on the Subject Diary Card. If a symptom is still present at Day 7, the date of the last day the symptom was present should be recorded.

Instructions for Recording Medicines Taken for Reactions and General Symptoms on the Day of Vaccination and/or on the First 6 days after Vaccination

The subject's parent(s)/LAR(s) should be advised to report any medications that were taken to treat any of the reactions or symptoms which occurred following the vaccination administration and for the next 3 weeks. With a tick box this should be recorded on the diary for the first 6 days after vaccination.

Other Solicited Adverse Events

The study staff must review the data entered into the Subject Diary Card as described in [section 3.4.2, Tools Used for Data Collection](#) and [section 5.3.1, Follow-up Clinic Visit\(s\)](#).

Note: Any solicited AE that meets any of the following criteria must be entered into subjects' source document (see [section 9.1, Source Documentation](#)) and also as an adverse event on the adverse event eCRF:

- Solicited local or systemic AE that leads to a visit to a health care provider (see [section 7.1.3, Evaluation of Adverse Events](#)).

- Solicited local or systemic AE leading to the subject withdrawing from the study or the subject being withdrawn from the study by the investigator (AE leading to withdrawal, see [section 7.1.3, Evaluation of Adverse Events](#)).
- Solicited local or systemic AE that otherwise meets the definition of a SAE (see [section 7.1.4, Serious Adverse Events](#)).

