Vaccine administration will be performed IM, anterolateral thigh for children ages < 2 years; deltoid for children ages \geq 2 years, unless insufficient deltoid mass. Each vaccine administration will be performed in an observer-blind manner (ie, efforts should be taken to shield the subject/parent(s)/LAR(s) and blinded study team members from the view of the vaccine administration). To maintain the observer-blind design of the study, the roles and responsibilities of “blinded” and “unblinded” team members will be defined and maintained. Safety assessments and study-related procedures and monitoring thereof must be performed by “blinded” team members.

After each vaccination, all subjects will remain under medical supervision at the study site for at least 30 minutes to be monitored and evaluated for AEs.

Subject Diary Cards will be provided to subjects for recording of local and systemic reactions for 7 consecutive days after each vaccination.

- From Day 1 through Day 7, and from Day 22 through Day 28, all solicited AEs, all unsolicited AEs (including SAEs, NOCDs, AEs leading to vaccine and/or study withdrawal, and AESIs), and associated concomitant medications for any of these events and vaccinations given within these periods will be recorded in the subject’s eCRFs.
- From Day 8 through Day 22 (before vaccination), and from Day 29 through Day 43 all unsolicited AEs (including SAEs, NOCDs, AEs leading to vaccine and/or study withdrawal, AESIs), solicited AEs that continue beyond Day 7 or Day 28 , respectively, and associated concomitant medications and all vaccinations given within these intervals will be recorded in the subject’s eCRF until the time of return to the clinic on Day 22, and Day 43,respectively in the subject’s eCRFs.

In the follow-up period (Day 44 through Day 387), only the following subset of unsolicited AEs and the associated concomitant medications/vaccinations will be collected and documented in the subject’s eCRFs: all SAEs, NOCDs, AEs leading to vaccine and/or study withdrawal, and AESIs (as described in [section 7.1](#) of the current protocol). These data will be captured by interviewing the subject’s parent(s)/LAR(s) and/or by reviewing the available medical records.

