7.1.3 Evaluation of Adverse Events

Every effort should be made by the investigator to evaluate safety information reported by a subject for an underlying diagnosis and to capture this diagnosis as the event on the AE page. In other words, the practice of reporting only symptoms (eg, "cough" or "ear pain") are better reported according to the underlying cause (eg, "asthma exacerbation" or "otitis media").

The severity of events reported on the adverse events eCRF will be determined by the investigator as:

Mild: transient with no limitation in normal daily activity.

Moderate: some limitation in normal daily activity.

Severe: unable to perform normal daily activity.

The relationship of the study treatment to an AE will be determined by the investigator based on the following definitions:

1. Not Related

The AE is not related to an investigational vaccine if there is evidence that clearly indicates an alternative explanation. If the subject has not received the vaccine, the timing of the exposure to the vaccine and the onset of the AE are not reasonably related in time, or other facts, evidence or arguments exist that reasonably suggest an alternative explanation, then the AE is not related.

2. Possibly Related

The administration of the investigational vaccine and AE are considered reasonably related in time and the AE could be explained by exposure to the investigational vaccine or by other causes.

3. Probably Related

Exposure to the investigational vaccine and AE are reasonably related in time and no alternative explanation has been identified.

The relationship of the study treatment to an unsolicited AE will be determined by the investigator.

Note: all solicited AEs from Day 1 to Day 7 will be considered Adverse Drug Reactions (ADRs). Grading for severity of solicited local and systemic AEs is described in [section 7.1.1, Solicited Adverse Events](#).

Adverse events will also be evaluated by the investigator for the co-existence of any of the other following conditions:

- “New Onset of Chronic Disease”: an AE that represents a new diagnosis of a chronic medical condition that was not present or suspected in a subject prior to study enrolment.
- Adverse events leading to withdrawal: AEs leading to study or vaccine withdrawal.

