8.1 Endpoints

8.1.1 Primary Endpoint(s)

8.1.1.1 Primary Safety Endpoint(s)

The measures for assessing safety and reactogenicity are as follows:

- Percentages of subjects with solicited local and systemic AEs¹⁰ that occur within 7 days following each vaccination and calculated for 4 time intervals after vaccination: 30 minutes, 1 through 3 days, 4 through 7 days, and 1 through 7 days.
- Percentages of subjects with any unsolicited AEs reported within 21 days after each vaccination within each vaccine group.
- Percentages of subjects reporting SAEs, NOCDs, AESIs, and AEs leading to vaccine and/or study withdrawal, as collected from Day 1 through Day 387.

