8.4.2.1.3 Analysis of Unsolicited Adverse Events

This analysis applies to all AEs occurring during the study, judged either as probably related, possibly related, or not related to vaccination by the investigator, recorded in AE eCRF, with a start date on or after the date of first vaccination. This analysis will include solicited AEs continuing beyond Day 7, which will be considered as possibly related AEs. AE starting prior to the first vaccination will only be listed. The original verbatim terms used by investigators to identify AEs in the eCRFs will be mapped to preferred terms using the Medical Dictionary for Regulatory Activities (MedDRA) dictionary. The AEs will then be grouped by MedDRA preferred terms into frequency tables according to system organ class.

All reported AEs, as well as AEs judged by the investigator as at least possibly related to study vaccine, will be summarized according to system organ class and preferred term within system organ class. These summaries will be presented by vaccination group. When an adverse event occurs more than once for a subject, the maximal severity and strongest relationship to the vaccine group will be counted.

Separate summaries will be produced for the following categories:

- SAEs
- AEs that are possibly or probably related to vaccine

- AEs of special interest
- New onset of chronic disease
- AEs leading to withdrawal from the study or the second vaccination

Data listings of all AEs will be provided by subject. In addition, AEs in the categories above will be provided as listed data.

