13.3 Unsolicited Adverse Events

This analysis applies to all ongoing solicited AEs beyond seven days after the vaccination, all unsolicited AE's occurring during the study, judged either as probably related, possibly related, or not related to vaccination by the investigator, recorded in the AE eCRF, with a start date on (but with onset after vaccination) or after the date of vaccination. AE starting prior to study vaccination will only be listed.

The original verbatim terms used by investigators to identify AEs in the eCRFs will be mapped to PTs using the MedDRA dictionary.

The AEs will then be grouped by MedDRA PTs into frequency tables according to SOC. All reported AEs, as well as AEs judged by the investigator as at least possibly related to study vaccine, will be summarized according to SOC and the PT within SOC. These summaries will be presented by the vaccination group. When an AE occurs more than once for a subject, the maximal severity and strongest relationship to the vaccine group will be counted.

The assignment to time intervals will be done by day of onset and not by days ongoing/persisting.

Statistical Analysis Plan, Protocol Number V87_30

06 MAY 2022 Final Version 1.0

The summaries will be presented by SOC and PT and different periods of onset depending on the category of events.

- From Day 1 to 21 days after the last vaccination:

- AE
- AE by maximum severity
- Related (i.e. at least possible) AE
- SAEs
- Related SAEs
- AESIs
- NOCD
- AEs leading to withdrawal (from the study or the second vaccination)
- Deaths.

- From Day 1 to end of study:

- SAEs
- Related SAEs
- AESIs
- NOCD
- AEs leading to withdrawal (from the study or the second vaccination)
- Deaths.

A summary of subjects with solicited and unsolicited non-serious treatment emergent adverse events reported by >5% of subjects sorted by system organ class and preferred term will be provided for clinicaltrials.gov and EudraCT.eu posting purposes.

Data listings of all AEs will be provided by the subject. In addition, AEs in the categories above will be provided as listed data.

Statistical Analysis Plan, Protocol Number V87_30

06 MAY 2022 Final Version 1.0

All tables will be produced overall and by age subgroup. The overview summary as well as the summary of AEs and SAEs will be also be presented by the other subgroups.

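### The Protocol 7.1.1 rule for entering solicited reactions on the AE eCRF names withdrawal from the study only, so a short reaction that leads to dose 2 not being given can miss the withdrawal table

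*Protocol*

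**What the plan says.** Protocol 7.1.1 sends a diary-card reaction to the AE eCRF if it lasts beyond Day 7, leads to a health care provider visit, meets the SAE definition, or falls under this item: "Solicited local or systemic AE leading to the subject withdrawing from the study or the subject being withdrawn from the study by the investigator". The item then labels the event as an AE leading to withdrawal and refers to 7.1.3.

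Protocol 7.1.3 defines that category more widely: "Adverse events leading to withdrawal: AEs leading to study or vaccine withdrawal".

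The primary safety endpoint in Protocol 8.1.1.1 is also wider: "Percentages of subjects reporting SAEs, NOCDs, AESIs, and AEs leading to vaccine and/or study withdrawal, as collected from Day 1 through Day 387".

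Both analysis sections follow the wider definition. Protocol 8.4.2.1.3 plans a summary of "AEs leading to withdrawal from the study or the second vaccination", and SAP 13.3 lists "AEs leading to withdrawal (from the study or the second vaccination".

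The source for the protocol analysis is AEs "recorded in AE eCRF, with a start date on or after the date of first vaccination". Protocol 3.8 describes the flag to be set on that form, and it covers withdrawal from the study only.

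**The concern.** The endpoint counts two outcomes, leaving the study and losing the vaccine. The rule that decides which diary reactions reach the form behind the table names only the first.

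The protocol expects the two outcomes to separate. Section 4.2 asks children who are not given dose 2 to complete the remaining visits and calls, and 4.4 encourages continued participation. A child can therefore lose dose 2 to a reaction without leaving the study.

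At stake is whether the withdrawal table, by system organ class and preferred term, counts what the endpoint defines, and whether sites record such events in the same way. The expected counts are small, so one event more or less visibly changes an arm's percentage.

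**Working it through.** The documents state no figure for AEs leading to vaccine withdrawal, so there is none to reproduce. The check is a comparison of texts, followed by a scale calculation.

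**1. Scope of withdrawal in each place**

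| Place | Study | Vaccine or dose 2 |
|---|---|---|
| Protocol 7.1.1, item wording | yes | not named |
| Protocol 3.8, AE eCRF flag | yes | not named |
| Protocol 7.1.3, definition cited by the 7.1.1 item | yes | yes |
| Protocol 8.1.1.1, primary endpoint | yes | yes |
| Protocol 8.4.2.1.3, summary | yes | yes |
| SAP 13.3, summary | yes | yes |

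**2. The case that can fall through**

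Take a solicited reaction after dose 1 and test it against the 7.1.1 triggers:
- It resolves by Day 7, so the duration trigger does not apply.
- It is not serious, so the SAE trigger does not apply.
- No provider was seen, so the visit trigger does not apply.
- Dose 2 is not given because of it, but the child stays in the study, so the words of the withdrawal item do not apply.

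Only the reference to 7.1.3 brings this reaction onto the AE eCRF through 7.1.1. All other solicited reactions that cost dose 2 get there by another trigger.

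**3. Counting once the event is on the form**

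Protocol 8.4.2.1.3 covers all AEs recorded on the AE eCRF. The opening of SAP 13.3 is narrower: unsolicited AEs, and solicited AEs that continue beyond seven days. A short solicited reaction entered because it led to withdrawal is not clearly within that scope. The SAP therefore needs a clause even if every site enters the event.

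**4. Scale**

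Planned numbers are 420 children, about 70 per arm and 35 per arm and age cohort (Protocol 6.1).
- One child in an arm: 1/70 = 1.43 percentage points.
- One child in an arm-by-age cell: 1/35 = 2.86 percentage points.

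Expected number missing from the AE eCRF = N × p × f. Here p is the proportion of children with the case in step 2, and f is the share of those not entered. The documents give neither, so both are assumptions, shown over a wide range:

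| p (assumed) | f (assumed) | Trial, N = 420 | Arm, N = 70 |
|---|---|---|---|
| any | 0 | 0 | 0 |
| 0.5% | 1 | 2.1 | 0.35 |
| 1% | 0.5 | 2.1 | 0.35 |
| 1% | 1 | 4.2 | 0.7 |
| 2% | 1 | 8.4 | 1.4 |
| 5% | 1 | 21 | 3.5 |

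f = 0 means that every site follows 7.1.3. f = 1 means that every site applies the 7.1.1 words literally and no other route captures the event.

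**The case against.** The strongest reply is that the 7.1.1 item carries its own correction: it refers to 7.1.3, which includes vaccine withdrawal. A site that follows the reference enters the event. This stands, and it is why no loss can be asserted.

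Other text points the same way:
- Protocol 3.1 has "all solicited AEs, all unsolicited AEs (including SAEs, NOCDs, AEs leading to vaccine and/or study withdrawal, and AESIs" recorded in the eCRFs.
- Protocol 7.1.2 has all AEs starting from Day 1 to Day 43 recorded in the eCRF.
- Protocol 5.3.1 requires AEs that parents report at Day 22 and Day 43 to go on the AE form, and Day 22 is when dose 2 would be withheld or refused.
- The Time and Events Table schedules assessment of AEs leading to withdrawal from the first visit onward, citing 7.1.3.
- Protocol 5.5.1 applies early-termination procedures, where possible, to a child withdrawn from treatment.

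These routes help but do not settle the matter. Section 3.1 does not name the form. Section 7.1.2 concerns unsolicited AEs. If either sent every diary reaction to the AE eCRF, the 7.1.1 list would have no purpose. Section 5.3.1 names the form, but it follows an interview about unsolicited AEs and defers to 7.1. Section 7.1.5 refers back to 7.1.1.

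It is also fair to say that much of the information is held elsewhere. The reaction is tabulated by arm as a solicited AE. Section 4.2 requires the reason for not giving a scheduled dose in the eCRF, and 8.4.1.1 plans a summary of reasons for withdrawal from vaccination. The reactogenicity comparison therefore does not depend on this item. But SAP 9.1 lists study withdrawals only and SAP 13.1 counts doses without reasons, so neither replaces the withdrawal table.

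A reader might infer that the endpoint is certain to be under-counted, that this is the main way children lose dose 2, or that arms are biased towards no difference. The documents support none of these. They give no rate, overall or by arm. Among the 4.4 criteria, related SAEs reach the AE eCRF anyway, and an immediate allergic reaction is not a diary term. A mild reaction that has resolved does not obviously meet any 4.4 criterion, so the remaining cases would mostly be parental refusal.

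**Conclusion.** The point holds as an inconsistency between a data-capture rule and the primary safety endpoint it serves. The 7.1.1 item and the 3.8 flag are narrower than 7.1.3, 8.1.1.1, 8.4.2.1.3 and SAP 13.3. A short, non-serious, unattended solicited reaction that leads to dose 2 not being given, in a child who stays in follow-up, can be left off the AE eCRF. It can also fall outside the stated scope of SAP 13.3.

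The data-capture loss lies between none and all of these few cases, depending on how sites read the text. Each affected child is about 1.4 points in an arm of 70 and 2.9 points in a cell of 35. The expected counts above rest on assumed rates and are for scale only. The study is descriptive with no success criterion, so no formal conclusion depends on this. It is worth correcting because recording of a primary endpoint should not depend on sites preferring a cross-reference to the item's explicit words.

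**What to change.** Reconcile the passages as follows.

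- **Protocol 7.1.1 and 3.8:** word the withdrawal item, and the matching AE eCRF flag, as *leading to withdrawal from the study or to the second study vaccination not being given*. Carry the same words into the eCRF completion guidance.
- **SAP 13.3:** count a child under AEs leading to withdrawal if an AE is shown as the cause in either of two places: any AE eCRF record, solicited or unsolicited and of any duration, or the eCRF reason for not giving dose 2. Section 4.2 already requires that reason, so it can identify children with no AE record.

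The cost is one clause in the protocol and guidance, one sentence in the SAP, and a few more AE eCRF entries. The change concerns recording and counting only. It proposes no rule on when dose 2 should be given or withheld.
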